2.4 Interim Analyses

Two interim data reviews and analyses will be scheduled and held promptly after the pertinent milestone has been reached. The first analysis will occur when 25% of the subjects have completed week 3. The first interim analysis will be a blinded analysis for drug safety only.

The second analysis will occur when 50% of the planned 24 COVID-19 cases have been reported (i.e., after 12 COVID-19 cases are reported). The second interim analysis will be for safety and potentially stopping the trial for futility. The Interim Data Review Plan will be included in the Independent Data Monitoring Committee (IDMC) charter.

Futility will be assessed via the efficacy of NTZ for the COVID-19 endpoint. The IDMC will recommend stopping for futility if the CMH test statistic for comparing the treatment groups on the COVID-19 endpoint is less than 0.179 (i.e., a p -value greater than 0.3278). The CMH test will be conducted for the sole purpose of evaluating futility; there will be no early stopping for efficacy. This bound was set using O'Brien-Fleming bounds for futility with overall $\alpha = 0.049$.

The IDMC will conduct the meetings in accordance with the IDMC charter. No efficacy analysis is planned and no allocation of α to the interim analysis is necessary.

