8.4.1. Efficacy Analyses

Efficacy analyses will be based on a population consisting of all subjects randomized without a laboratory-detected viral respiratory infection at the baseline visit (intention-

to-treat or ITT population). All chi-square analyses will be calculated with appropriate continuity corrections.

There will be two primary efficacy analyses:

- The proportion of subjects experiencing COVID-19 in the NTZ treatment group will be compared to that of the placebo treatment group using a two-sided Cochran-Mantel-Haenszel (CMH) chi-square test ($\alpha = 0.049$).
- The proportion of subjects experiencing VRI in the NTZ treatment group will be compared to that of the placebo treatment group using a two-sided CMH chi-square test ($\alpha = 0.001$).

Secondary analyses will be performed as follows:

- The proportion of subjects experiencing COVID-19 or VRI for treatment vs control will be tested within strata using Pearson chi-square tests at an unadjusted $\alpha = 0.05$.
- Confidence intervals (95% confidence level) will be produced for the overall odds ratio and for the odds ratios for NTZ vs placebo for each stratum.
- Proportions of subjects experiencing mortality due to COVID-19 or complications thereof will be compared by treatment group using a two-sided Pearson chi-square test (unadjusted $\alpha = 0.05$).
- Proportions of subjects (with or without symptoms) testing positive for antibodies to SARS-CoV-2 at either of the Week 6 or Week 8 visits will be compared by treatment group using a two-sided Pearson chi-square test (unadjusted $\alpha = 0.05$).

Exploratory analyses will be performed as follows:

- Proportions of subjects experiencing each of the following will be compared by treatment group using a two-sided Pearson chi-square test (unadjusted $\alpha = 0.05$): (i) hospitalization due to VRI or complications thereof, (ii) mortality due to VRI or complications thereof, (iii) proportions of subjects experiencing acute respiratory illness (ARI), (vi) hospitalization due to ARI or complications thereof, (v) mortality due to ARI or complications thereof.

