14. MONITORING THE STUDY

Monitoring will be conducted by the Sponsor and/or a contract research organization according to standard operating procedures. Site visits will be conducted on-site or remotely by the Sponsor or their representatives at regular intervals to conduct inspections.

A full description of the monitoring procedures for this study will be detailed in the Clinical Monitoring Plan.

The Investigator will grant representatives of the Sponsor's clinical operations team and quality team, as well as regulatory agencies and ethical committees access to inspect facilities and records (including subject charts) relevant to this study and agrees to assist the monitors in their activities, if requested.

An Independent Data Monitoring Committee (IDMC) will be organized to monitor safety and futility for this study. A full description of the IDMC procedures for this study will be detailed in the Medical Monitoring (Safety) Plan and IDMC Charter.

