4.2 Efficacy Analysis

4.2.1 Primary Efficacy Variables

This study has two primary endpoints: symptomatic COVID-19 disease and symptomatic VRI. The study-wise Type I error rate is 0.05, allocated $\alpha = 0.049$ to COVID-19 disease and $\alpha = 0.001$ to all VRI. In each case the hypotheses to be tested are

$$\begin{aligned}H_0: p_1 &= p_2 \\H_1: p_1 &\neq p_2,\end{aligned}$$

where p_1 represents the COVID-19 disease rate (or VRI rate) in the NTZ arm and p_2 represents the COVID-19 disease rate (or VRI rate) in the placebo arm.

Primary Analysis

The proportion of subjects experiencing symptomatic COVID-19 disease in the NTZ treatment group will be compared to the similar proportion in the placebo group using a two-sided CMH test with continuity correction at $\alpha=0.049$. The contingency tables will be provided with rates relative to the treatment margins. The common relative risk and the odds ratio between the treatment groups and 95% confidence intervals for these parameters will be provided. The analysis will be repeated by sex of subject (female or male), age group of subjects (18- 34 years, 35- 64 years, 65 years and older), and race of subject (white or non-white).

The proportion of subjects experiencing symptomatic VRI infections in the NTZ treatment group will be compared to the similar proportion in the placebo group using a two-sided CMH Chi-square test with continuity correction at $\alpha=0.001$. The contingency tables will be provided with rates relative to the treatment margins. The common relative risk and the odds ratio between the treatment groups and 95% confidence intervals for these parameters will be provided. The analysis will be repeated by sex of subject (female or male), age group of subjects (18- 34 years, 35- 64 years, 65 years and older), and race of subject (white or non-white).

While every effort will be made to compile the data in accordance with intent-to-treat, it is likely that some subjects will have missing endpoints. Subjects with missing outcomes data will be included in the primary analysis. The primary analysis will impute missing data as uninfected in each treatment arm. Best-case and worst-case sensitivity analyses will be performed as outlined in Section 2.3 above. In addition, a tipping point analysis will

be performed, imputing various levels of COVID-19 and VRI infection rates to missing values in the NTZ arm to determine the infection rate at which the study conclusions change.

Secondary Analysis

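### The futility rule in SAP 2.4 gives two thresholds that are not equivalent, and it has no direction, so a marked excess of COVID-19 on NTZ does not trigger it

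*SAP*

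**What the plan says.** SAP 2.4 plans a second interim look at 12 of the planned 24 COVID-19 cases: "The second interim analysis will be for safety and potentially stopping the trial for futility". The criterion is "Futility will be assessed via the efficacy of NTZ for the COVID-19 endpoint". The IDMC recommends stopping "if the CMH test statistic for comparing the treatment groups on the COVID-19 endpoint is less than 0.179", which a parenthesis opening with i.e. equates to a p-"value greater than 0.3278". The bound is attributed to an O'Brien-Fleming futility boundary with overall α = 0.049. There is no early stopping for efficacy. Section 2.4 gives no type II error, spending function, sign convention or statement on continuity correction, and it places the Interim Data Review Plan in the IDMC charter, which is not among the documents.

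Elsewhere the CMH test is a two-sided chi-square. In SAP 4.2.1 the COVID-19 proportion on NTZ is "compared to the similar proportion in the placebo group using a two-sided CMH test with continuity correction at" α = 0.049. Protocol 8.4.1 says: "All chi-square analyses will be calculated with appropriate continuity corrections". Protocol 14 confirms the committee's remit: "An Independent Data Monitoring Committee (IDMC) will be organized to monitor safety and futility for this study".

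**The concern.** The i.e. presents the two numbers as one rule on two scales. If they do not correspond, the same 12 cases can produce a recommendation to stop under one number and to continue under the other, and the plan does not say which governs.

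The second problem is direction. The stated aim is to judge efficacy of NTZ, but a CMH chi-square is squared and cannot tell fewer cases on NTZ from more. A rule that stops when the statistic is small therefore stops near an even split and continues when NTZ has clearly more cases, which is the strongest evidence of futility.

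**Working it through.** **Inputs.** Thresholds 0.179 and 0.3278, look at 12 of 24 cases, α = 0.049 (SAP 2.4); 1:1 allocation and seven strata (SAP 1.1); planned relative risk 0.2, from an 80% reduction (SAP 1.3); continuity correction (SAP 4.2.1, Protocol 8.4.1). Assumed here: equal arms and collapsed strata; stratified checks follow.

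**1. Do the two thresholds match?** For a chi-square on 1 df:

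- P(χ² > 0.179) = 0.6722, the p-value that belongs to 0.179.
- P(χ² < 0.179) = 0.32777, which rounds to the printed 0.3278.
- The chi-square with p = 0.3278 is 0.958.
- Read as a one-sided p from a signed Z, 0.3278 gives Z = 0.446 and Z² = 0.199. Conversely √0.179 = 0.423 has one-sided p = 0.336. This is close but not equal, although no split of 12 cases falls between 0.179 and 0.199.
- Read as a Z, 0.179 gives p = 0.429 one-sided or 0.858 two-sided. With 2 to 7 df, p is 0.914 or more.

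No reading makes the pair equal. The four-decimal match with the lower tail makes a 1 − p slip more likely than a one-sided reading.

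**2. What does each threshold do at 12 cases?** With x cases on NTZ, χ² = (max(|x − 6| − 0.5, 0))² / 3; the uncorrected form drops the 0.5.

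| NTZ:placebo | χ² corrected (p) | < 0.179 | p > 0.3278 | χ² uncorrected (p) | < 0.179 | p > 0.3278 |
|---|---|---|---|---|---|---|
| 6:6 | 0.00 (1.00) | stop | stop | 0.00 (1.00) | stop | stop |
| 5:7 or 7:5 | 0.083 (0.773) | stop | stop | 0.333 (0.564) | continue | stop |
| 4:8 or 8:4 | 0.750 (0.387) | continue | stop | 1.333 (0.248) | continue | continue |
| 3:9 or 9:3 | 2.083 (0.149) | continue | continue | 3.00 (0.083) | continue | continue |

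More extreme splits in either direction also continue. The thresholds conflict at 4:8 and 8:4 with the correction, and at 5:7 and 7:5 without it.

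**3. Stopping probabilities.** Cases on NTZ ~ Binomial(12, RR/(1 + RR)), corrected statistic.

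- At RR 0.2 the NTZ share is 1/6. P(5) + P(6) + P(7) = 0.0284 + 0.0066 + 0.0011 = 3.6% after rounding. Adding P(4) = 0.0888 and P(8) = 0.0001 gives 12.5%.
- At RR 1: (792 + 924 + 792)/4096 = 61%. Adding 2 × 495 gives 3498/4096 = 85%.

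| True RR | Stop, χ² < 0.179 | Stop, p > 0.3278 |
|---|---|---|
| 0.2 | 3.6% | 12.5% |
| 1 | 61% | 85% |
| 2 | 35% | 60% |
| 3 | 15% | 35% |

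Stopping becomes less likely as harm grows.

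**4. Power at 24 cases, RR 0.2.** The final corrected test needs χ² > 3.875, which is met in favour of NTZ at 6 or fewer of 24 cases. Power sums, over interim splits that continue, the binomial probability of ending at 6 or fewer. It is 90.9% with no interim, 89.7% with 0.179 and 83.7% with p > 0.3278, so the choice of threshold moves power by 6.0 points. Without the correction, false stops are 0.7% and 3.6%, and power is 96.2% and 94.3% (96.5% with no interim). These are exact-binomial figures, not the plan's own CMH power figures.

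**5. Strata.** Simulation with seven equal strata gives false-stop rates of 3.6–3.7% and 12.5–12.6%. Unequal strata with chance arm imbalance give 1.4–4.1% and 5.4–13.5%.

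**6. Where 0.179 may come from.** If 90% power is assumed, an O'Brien-Fleming-type futility bound at half information and α = 0.049 has Z² of 0.182–0.184 (binding) or 0.196–0.197 (non-binding). A Lan-DeMets form, or 80% power, moves it further away. Nothing tried gives 0.179 exactly.

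**The case against.** **0.179 is evidently the bound and the parenthesis is only a conversion slip.** This is probably right: the lower-tail match and the nearby 90%-power bound both favour it. If 0.179 governs, power falls only from 90.9% to 89.7%. But SAP 2.4 does not tie 90% power to the bound, no calculation returns 0.179 exactly, and an IDMC member reading the printed p-value would apply a materially different rule.

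**The size depends on the continuity correction, which SAP 2.4 does not mention for the interim.** This stands as a condition. Without the correction the power difference is about 2 points rather than 6, and the conflict moves to 5:7 and 7:5. It does not vanish on either reading, and the analysis sections point to the corrected test.

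**A symmetric futility region suits a two-sided hypothesis.** It can be defended as stopping when neither direction looks demonstrable. SAP 2.4, however, defines futility by efficacy of NTZ, and a rule that stops at 6:6 but continues at 10:2 against the drug does not serve that aim. The safety review at the same look could still act on such an excess, and the charter may add a direction. The safety route is only a partial answer, because Protocol 10 keeps symptoms and complications of VRIs out of adverse event reporting.

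**The interim is probably past.** Protocol 3 expects the study to end in April 2021 and the SAP is dated 26 April 2024. The documents do not say whether the look took place. If it did, the rule should not now be changed, but the record still needs to show which threshold was used.

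**Conclusion.** The concern holds on both counts and must be fixed. The mismatch between 0.179 and 0.3278 is a matter of tail areas and rests on no design assumption. Nor does the lack of direction: a split of 9:3 or worse against NTZ meets neither threshold, corrected or not.

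The operating figures (false stop 3.6% versus 12.5%, power 89.7% versus 83.7%) assume 12 and then 24 cases, equal arms, collapsed strata, RR 0.2 and the continuity correction. Type I error is not inflated, because there is no efficacy stop. The intended bound cannot be settled from the documents, and the charter could change how the rule operates in practice.

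**What to change.** State one threshold on one scale and correct the other to match. If 0.179 is kept, the matching two-sided condition is p > 0.6722; if p > 0.3278 was intended, the matching chi-square is 0.958.

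Apply it to the signed CMH Z, positive when NTZ has fewer cases, so that any result with no fewer cases on NTZ also meets the rule. Signed Z < 0.423 restates 0.179 (√0.179), and signed Z < 0.979 restates 0.958 (√0.958). The sponsor should confirm the value against its O'Brien-Fleming derivation, giving the type II error, the spending function and whether the interim statistic is continuity-corrected. Align the IDMC charter, and restate power with the boundary included.

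If the look has already taken place, do not alter the rule retrospectively; document which threshold the IDMC applied and the result.

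The cost is wording in the SAP and charter, with no patients and no α. With the correction, a directional rule stops at RR 2 in 98% (0.179) or 99.6% (0.958) of trials, and power at RR 0.2 stays at 89.7% or 83.7%. It also stops more often when there is no effect: 81% instead of 61% for 0.179, and 93% instead of 85% for p > 0.3278. Without the correction that increase is larger for 0.179, 61% instead of 23%, and the stopping rate at RR 2 is 93%.

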2.5 Study Center Considerations in the Data Analysis

A study center is defined as a treatment administration site or group of treatment administration sites under the control and supervision of the same Principal Investigator (PI). There will be no selective pooling of study centers – all sites will be pooled. The study is planned to be conducted at multiple sites.

2.6 Documentation and Other Considerations

The data analyses will be conducted using Python and supported statistical packages.

3.0 Analysis of Baseline Patient Characteristics

Baseline and demographic characteristics of the safety population will be summarized. Continuous variables (age and baseline weight) will be summarized via mean, standard deviation, minimum, median, maximum, and number of non-missing responses. Categorical variables (gender, race ethnicity, and tobacco use (by product type)) will be summarized via counts and percentages.

A detailed listing of baseline data for each patient in the safety population will also be provided as shown in Appendix B.

4.0 Analysis of Efficacy

4.1 Efficacy Variables

All the efficacy variables are categorical in nature: the presence or absence of any VRI, ARI, or COVID-19 during the study period. Similarly, hospitalization (and its cause) and death (and its cause) are categorical.

Primary Efficacy Variables

There are two primary efficacy variables:

1. The presence or absence of symptomatic COVID-19 disease identified after the start of treatment and before the end of the 6-week treatment period.
2. The presence or absence of symptomatic VRI (including COVID-19) identified after the start of treatment and before the end of the 6-week treatment period.

Symptomatic COVID-19 is defined as an ARI after start of treatment and before the end of the 6-week treatment period associated with detection of SARS-CoV-2 by RT-PCR assay of nasopharyngeal swab.

Symptomatic VRI is defined as an ARI after start of treatment and before the end of the 6-week treatment period associated with detection of any respiratory virus by RT-PCR assay of nasopharyngeal swab.

A subject will be considered to have met the criteria for an ARI if:

1. The subject meets the criteria that trigger the Suspected ARI Visit (see Section 1.2);

AND

2. The subject satisfies the following ARI definition: ARI is defined as ≥ 0.5 increase from baseline in mean symptom score for the FLU-PRO[®] chest/respiratory domain alone; or a ≥ 0.5 increase from baseline in mean symptom score for at least two of the following FLU-PRO[®] domains: body/systemic, nose, throat.

Secondary Efficacy Variables

The secondary efficacy variables are:

1. Mortality due to COVID-19 or complications thereof.
2. The presence or absence of anti-SARS-CoV-2 antibodies at either of the Week 6 or Week 8 visits.

Exploratory Efficacy Variables

The exploratory efficacy variables are:

1. Hospitalization due to VRI or complications thereof.
2. Mortality due to VRI or complications thereof.
3. Presence or absence of an ARI.
4. Hospitalization due to ARI or complications thereof.
5. Mortality due to ARI or complications thereof.

4.2 Efficacy Analysis

4.2.1 Primary Efficacy Variables

This study has two primary endpoints: symptomatic COVID-19 disease and symptomatic VRI. The study-wise Type I error rate is 0.05, allocated $\alpha = 0.049$ to COVID-19 disease and $\alpha = 0.001$ to all VRI. In each case the hypotheses to be tested are

$$\begin{aligned}H_0: p_1 &= p_2 \\H_1: p_1 &\neq p_2,\end{aligned}$$

where p_1 represents the COVID-19 disease rate (or VRI rate) in the NTZ arm and p_2 represents the COVID-19 disease rate (or VRI rate) in the placebo arm.

Primary Analysis

The proportion of subjects experiencing symptomatic COVID-19 disease in the NTZ treatment group will be compared to the similar proportion in the placebo group using a two-sided CMH test with continuity correction at $\alpha=0.049$. The contingency tables will be provided with rates relative to the treatment margins. The common relative risk and the odds ratio between the treatment groups and 95% confidence intervals for these parameters will be provided. The analysis will be repeated by sex of subject (female or male), age group of subjects (18- 34 years, 35- 64 years, 65 years and older), and race of subject (white or non-white).

The proportion of subjects experiencing symptomatic VRI infections in the NTZ treatment group will be compared to the similar proportion in the placebo group using a two-sided CMH Chi-square test with continuity correction at $\alpha=0.001$. The contingency tables will be provided with rates relative to the treatment margins. The common relative risk and the odds ratio between the treatment groups and 95% confidence intervals for these parameters will be provided. The analysis will be repeated by sex of subject (female or male), age group of subjects (18- 34 years, 35- 64 years, 65 years and older), and race of subject (white or non-white).

While every effort will be made to compile the data in accordance with intent-to-treat, it is likely that some subjects will have missing endpoints. Subjects with missing outcomes data will be included in the primary analysis. The primary analysis will impute missing data as uninfected in each treatment arm. Best-case and worst-case sensitivity analyses will be performed as outlined in Section 2.3 above. In addition, a tipping point analysis will

be performed, imputing various levels of COVID-19 and VRI infection rates to missing values in the NTZ arm to determine the infection rate at which the study conclusions change.

Secondary Analysis

Secondary analyses of the primary endpoints include the proportion of subjects experiencing symptomatic COVID-19 in the NTZ treatment group will be compared with the similar proportion in the placebo group for each stratum using a Pearson Chi-square test with continuity correction. A 95% Wilson confidence interval (with continuity correction) will be produced for the symptomatic COVID-19 infection in each group within each stratum. A 95% confidence interval for the odds-ratio of symptomatic COVID-19 infection rate in the NTZ vs placebo groups will be produced for each stratum. The contingency tables will be provided with rates relative to the treatment margins.

4.2.2 Secondary Efficacy Variables

Statistical tests for the secondary efficacy variables will be performed only if the primary analyses of primary efficacy variables both reject the null hypothesis. These tests act as gatekeepers to the secondary efficacy tests. No allocation of study-wise α to the secondary tests is necessary.

The mortality rates due to COVID-19 or complications will be compared by stratum with a Pearson Chi-square test. The overall mortality rate due to COVID-19 or complications in the two treatment groups will each be compared using a CMH Chi-square test with continuity correction at $\alpha=0.05$. A 95% confidence interval for the pooled odds-ratio will be provided.

The proportion of subjects testing positive for SARS-CoV-2 antibodies at either Week 6 or Week 8 will be compared using Pearson Chi-square tests with continuity correction in each stratum. The contingency tables will be provided with rates relative to the treatment margins. The overall positive rates in the treatments will be analyzed with a CMH Chi-square test.

4.2.3 Exploratory Efficacy Variables

Hospitalization due to VRI or complication thereof, mortality due to VRI or complications thereof, presence of an ARI, hospitalization due to ARI or complications thereof, and mortality due to ARI or complications thereof will each be summarized in a three-way contingency table (Stratum*Treatment*Variable) with counts and percentages relative to the table row margins. Pearson chi-square test results per stratum will be provided as will a CMH Chi-square test of treatment effects and a 95% confidence interval for the pooled odds ratio for the NTZ vs placebo group.

5.0 Analysis of Safety

5.1 Description of Safety Variables

The safety analysis variables are defined as follows:

- Adverse Events (AEs).
- Clinical Laboratory Values (Hematology, Blood Chemistry, and Urinalysis).
- Physical Exam.
- Vital Signs.

The following describes the safety analyses to be performed for the study. All safety analyses will be performed on the safety population.

